15.1.3 Methods for Evaluation of Measurable Disease

Pancreas protocol CT or chest abdomen pelvis CT (biphasic imaging, 1.25 mm cuts) will be obtained at follow-up intervals as described in Section 14. Study Calendar. PET-CT scans should be done at baseline (pre-study) and repeated if possible at the 3-month follow-up.

Standard radiographic criteria will be utilized for non-target lesions. Any disease outside of the pancreas will be considered metastatic disease. If possible a biopsy should be obtained to confirm metastasis.

15.1.4 Duration of Response

The criteria for overall response will be the time from randomization and first sign of local progression or development of metastatic disease.

15.1.5 Progression-Free Survival (or other time-to-event parameters)

The criteria for time to progression and progression-free survival (PFS) will be the time from randomization to documented progression or death. Individuals will be censored at the date of last evaluation for progression if neither event is observed. Overall survival will be defined as time from randomization until death from any cause. Participants will be censored at the date of last contact if the date of death is not observed. Local PFS will be the duration from randomization to local progression or death if death occurs before local progression. Metastasis free survival will be the duration from randomization to metastasis or death from any cause, if death occurs before metastasis. Individuals will be censored at the time of the last evaluation for local or distant progression, respectively, if neither progression nor death is observed.

15.1.6 Response Review

All responses will be reviewed independently by a board certified radiologist at the study's completion. Each image will be reviewed by the PI from each institution periodically and recorded to assess for variability. Simultaneous review of the patient's chart will also occur at this time.

16. MONITORING PLAN AND DATA MANAGEMENT

16.1 Monitoring Plan

Stanford will serve as the coordinating institution and will conduct study audits to review each participating centers' regulatory binders and patient study charts. These

audits will ensure guidelines set forth in this protocol are followed for all aspects of the study including but not limited to regulatory approvals and renewals; patient eligibility, enrollment, treatment, and follow-up; proper documentation and record-keeping; and adverse event and deviation reporting. Audits will be performed yearly by Stanford DSMC; more frequent monitoring will occur as needed. Preliminary reviews may also take place by Stanford research staff prior to audits.

[figure not shown]
Each participating center will create and maintain a paper chart for each subject enrolled. Research staff at each center will also enter subject information into REDCap as per guidelines set forth in this protocol.

Participating centers will supply radiation treatment plan data upon request by uploading scan images and information. If uploading is not possible, images and reports may be supplied electronically or on encrypted and/or password-protected discs or drives. Further data may be requested from each institution for study analyses.

All tools, computers, and systems used for monitoring and analyses will be secure, password-protected, and HIPAA compliant. Shared data will be de-identified and unique identifiers will be assigned to ensure patient confidentiality.

See below diagram for phases and workflow of study.

16.2 **Study Diagram**

16.3 Trial Monitoring

All outcome data (toxicity and efficacy) will be reviewed yearly by the Principal Investigator and key Co-Investigators. This study will also be monitored by the Stanford DSMC as stated above in Section 16.1.

Interim reports and/or study renewals will be completed every 10-12 months from study open date, which will be defined as date the study is approved by Stanford IRB. Additional and/or more frequent reports may be done if determined necessary by the study monitoring group (described in Section 11.2.3). These reports may include information about:

- Patient accrual and follow-up: overall and at each institution
- The frequency and severity of adverse events due to protocol therapy
- Compliance rates of treatment delivery with respect to the protocol prescription

Adverse event rates will be compared between treatment groups and with the stopping guideline thresholds (Section 17.5.1). With the exception of a single, planned interim efficacy analysis (Section 17.5.2), the interim reports will not contain the results from the treatment comparisons with respect the primary outcome (progression free survival) or secondary efficacy analyses. See Section 17.5 Stopping Guidelines for additional details.

16.4 Data Management

Study and subject information will be entered and maintained in REDCap database. Research Coordinators at participating institutions will be given access to REDCap and enter data directly. Access will be created once the participating center has obtained all regulatory approvals and becomes a participating center in the study. Once REDCap access is established, research staff at each participating center will be provided educational materials or training on its use.

Participating centers can only view and enter data from their institution; Stanford research staff will have access to study and subject data from all participating centers.

Sections or topics required for entry in REDCap include but are not limited to:

- Diagnosis and Pathology
- Demographics
- Consent
- Eligibility
- On-Study Information
- Off-Study Information
- Arm Assignment/Randomization
- Chemotherapy dates, doses, and modifications as applicable
- Deviations
- SAEs and AEs
- Consultation information
- Pertinent medications
- Results of scans, laboratory and other tests

- Quality of Life responses

Other information for entry into REDCap may be requested or added.

Each center must also begin a patient paper study chart to collect and maintain subjects' records and study-related documents. Patient study charts may be reviewed by Stanford research team or Stanford DSMC to ensure data validity, integrity, and safety of subjects throughout the trial.

Shared data will be de-identified and unique identifiers will be assigned to ensure patient confidentiality.

16.4.1 Monitoring and Study Data Review

When all participating institutions have successfully received IRB approval *and* started enrolling patients, teleconferences will be held every 2 months between research staff from the Coordinating Center and each participating institution. A study monitoring group consisting of PIs and/or Research Coordinators from Stanford University, Johns Hopkins, and Memorial Sloan Kettering will discuss and monitor study-related events and issues in these calls. Included in this monitoring Group are:

- [name], Stanford
- [name], Stanford
- [name], and [name] Anderson

Discussions may include enrollment and accrual information; data updates and entry issues; adverse events, deviations, or patient-related issues; and other study-related matters. Calls may occur more frequently as needed. Data review and updates will also occur with analysis and completion of Interim Reviews as required per protocol.

16.5 Confidentiality

Study data will be maintained in password protected databases, computer, and/or electronic files. Only research personnel listed on this protocol will have access to this information. Only the patients unique IDN will be used. Specimens will be stored under the patient's IDN. The patient's name or other public identifiers will not be included in any information shared with other investigators.

17. STATISTICAL CONSIDERATIONS

17.1 Endpoints

17.1.1 Primary Endpoints

- To compare the median progression free survival between individuals treated

with mFOLFIRINOX +/- SBRT.

17.1.2 Secondary Endpoints

- To compare the one year progression-free survival in pancreatic cancer patients following chemotherapy alone or chemotherapy and SBRT.
- To compare metastasis free survival in pancreatic cancer patients following chemotherapy alone or chemotherapy and SBRT.
- To compare the overall survival in pancreatic cancer patients treated with chemotherapy alone or chemotherapy and SBRT.
- To compare local progression-free survival in pancreatic cancer patients after chemotherapy +/- SBRT.
- To evaluate acute (within 3 months of treatment) grade 2 or greater gastritis, fistula, enteritis, or ulcer and any other grade 3-4 gastrointestinal toxicity within 3 months of treatment.
- To identify new biomarkers in pancreatic cancer.
- To evaluate the quality of life of patients before and after either chemotherapy alone or chemotherapy and SBRT.

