Another phase II study treated locally advanced pancreatic cancer patients with gemcitabine followed by 25 Gy of SBRT delivered with Cyberknife and maintenance gemcitabine chemotherapy. In this study, the excellent progression free survival was confirmed from previous studies (81%). The median overall survival was 11.4 months, median time to progression was 9.7 months and 1 year survival was 50%(14). There were no significant acute GI toxicities however, of the 15 patients alive >6 months after SBRT, 7 (47%) experienced Grade 2 or greater GI toxicity, with 2 (13%) of the 15 experiencing Grade 3 or greater GI toxicity.

More recently, another phase II study of 25 Gy in a single fraction using a linac-based approach (Trilogy™, Varian Medical Systems, Palo Alto, CA) integrated with gemcitabine chemotherapy resulted in a 50% overall survival at 1 year and a 94% freedom from local progression at 1 year. Four patients (15%) developed Grade 2 ulcers and 1 patient (5%) developed a duodenal perforation (Schellenberg et al, IJROBP 2011).

Recently, we completed a multi-center phase II trial demonstrating the efficacy of SBRT (33

Gy in 5 fractions) in combination with gemcitabine chemotherapy. No significant toxicities were observed and median overall survival was 18 months. These data compare favorably to other studies reported in the literature. Based upon these promising data, we hypothesize that adding SBRT to a more aggressive systemic chemotherapy (FOLFIRINOX), will result in further improvement in OS in patients with locally advanced pancreatic cancer.

The proposed randomized study is a logical extension of the previously reported studies and will establish the efficacy of adding SBRT to FOLFIRINOX chemotherapy. Our prior multi-center phase II experience demonstrated the feasibility and efficacy of this approach in patients with locally advanced pancreatic cancer.

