7.5 Criteria for Removal from Study

Patients will be withdrawn from the study for any of the following reasons:

- disease progression (as defined in Section 15.1.2 Disease Parameters)
- patient withdrawal
- pregnancy
- patient noncompliance, or failure of the patient to follow instructions of the study staff
- protocol director decides that continuing participation could be harmful to the patient
- treatment needed for patient that is not allowed in the study
- patient is deemed resectable and proceeds to surgery
- study cancellation
- other administrative reasons
- unanticipated circumstances.

Patients will continue mFFX on-study until one of these endpoints; in the event of intolerable toxicity from mFFX, subjects will still be followed per protocol although chemotherapy may be altered or discontinued, the decisions of which will be left to the treating Medical Oncologist.

Patients withdrawn from the study will be followed for overall survival only.

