17.3.3 Criteria for Future Studies

We anticipate that fractionated SBRT with IGRT based linac systems will result in similar progression free survival at one year (80-90%) to single fraction SBRT but with a (20%) decrease in late gastrointestinal toxicity at one year. The current patient population will serve as a comparator for the future trials in terms of time to progression and provide additional information with regards to radiation treatment planning.

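### The only toxicity endpoint stops at 3 months from an undefined start, leaves out fatal GI events outside four named conditions, and has no later counterpart

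*Combined protocol and SAP*

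**What the plan says.** Section 17.1.2 lists one toxicity endpoint, worded the same way in section 1.2 and the synopsis: "To evaluate acute (within 3 months of treatment) grade 2 or greater gastritis, fistula, enteritis, or ulcer and any other grade 3-4 gastrointestinal toxicity". The 3-month limit is then repeated. The endpoint has two parts: four named conditions counted from grade 2 upward, and all remaining GI toxicity counted at grades 3 and 4. No late-toxicity endpoint is listed.

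Section 2.2 describes an earlier phase II study of gemcitabine with 25 Gy SBRT. It found nothing of note in the acute period, but for longer survivors it reports "of the 15 patients alive >6 months after SBRT, 7 (47%) experienced Grade 2 or greater GI toxicity, with 2 (13%) of the 15". The two patients in that last count had toxicity of grade 3 or worse.

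Other safety provisions:

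- Section 17.5.1 sets a stopping guideline on grade 3 or higher toxicity over the first 6 months.
- The study calendar (section 14) schedules adverse event evaluation at 3, 6, 9 and 12 months from completion of study treatment and beyond.
- Section 17.4 tabulates adverse events by type and grade at each follow-up.
- Section 7.5 lists disease progression and surgery among the reasons for removal, and then says "Patients withdrawn from the study will be followed for overall survival only".

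**The concern.** The question for this trial is whether adding SBRT to mFFX is worthwhile. Any gain in progression-free survival has to be read against GI toxicity, and 17.1.2 fixes how that toxicity will be reported. As worded, the endpoint could give an incomplete picture in three ways:

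- The 3-month window can be started at different moments in the two arms.
- A death from some of the severe radiation effects that the protocol names would not count.
- The window closes early, whereas the protocol's own earlier cohort reported little acute GI toxicity and appreciable GI toxicity among longer survivors.

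The later data needed to complete the picture are largely scheduled, but no endpoint or by-arm summary is defined for them.

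**Working it through.** **1. The cited cohort (section 2.2).** Inputs: 7 and 2 events among 15 patients alive more than 6 months after SBRT.

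- Proportions: 7/15 = 46.7% and 2/15 = 13.3%. Both match the stated 47% and 13%.
- Exact (Clopper-Pearson) 95% limits for x events in n: lower = the 0.025 quantile of Beta(x, n − x + 1); upper = the 0.975 quantile of Beta(x + 1, n − x).
- x = 7: Beta(7, 9) gives 0.213 and Beta(8, 8) gives 0.734, so 21–73%.
- x = 2: Beta(2, 14) gives 0.017 and Beta(3, 13) gives 0.405, so 2–40%.

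The intervals are wide. They support a qualitative contrast with the acute period, not an expected rate for this trial.

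**2. Which grades count.**

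| Event | Endpoint, 17.1.2 | Guideline, 17.5.1 |
|---|---|---|
| Gastritis, fistula, enteritis, ulcer | Grade 2 and up, grade 5 included | Grade 3 and up |
| Any other GI toxicity | Grades 3 and 4 only | Grade 3 and up |

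The risk information in section 6.2.1 names GI obstruction, perforation and hemorrhage as the severe radiation effects. None is among the four named conditions, so all three fall in the second row. A fatal one is outside the endpoint unless it was also recorded as one of the four, or at grade 3 or 4 before death. Perforation is not hypothetical: section 2.2 reports one duodenal perforation in another single-fraction cohort.

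**3. Where the window starts.** SBRT is five fractions in five days, or over up to two weeks (section 6.2). mFFX continues until a removal criterion is met (section 7.5). The calendar counts follow-up from completion of study treatment. Three months of treatment could therefore run from randomization, the first fraction, the last fraction, the first post-randomization cycle or the last cycle. The control arm has no SBRT date at all. Only randomization is defined alike in both arms.

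**4. What covers the later period.**

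| Source | Reach | By-arm cumulative estimate? |
|---|---|---|
| Endpoint, 17.1.2 | 3 months | Not specified |
| Stopping guideline, 17.5.1 | 6 months | No; a count against a boundary for SBRT-related events |
| Visit tables, 14 and 17.4 | 12 months and beyond, until removal | No; separate tables with changing denominators |
| After removal, 7.5 | Survival only | No adverse event collection stated |

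**The case against.** The strongest reply is that the endpoint is openly labelled acute and that later safety data are planned. Adverse events are assessed at every follow-up visit and mFFX cycle (sections 11.3 and 14), and section 6.2.1 allows RTOG grading of chronic effects. Interim reports compare adverse event rates between arms (section 16.3). Fatal events are reported as SAEs (section 11.1) and have an item on the case report form (Appendix V). This stands. The gap lies in the endpoint and its summary, not in data collection before removal. It does not remove the gap, because nothing says how the visit tables become one estimate per arm.

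The second reply is that 15 survivors of single-fraction 25 Gy with gemcitabine are a weak guide to 40 Gy in 5 fractions with mFFX. The protocol also cites 33 Gy in 5 fractions with no significant toxicity (section 9.1.3; an 8% grade 3–4 rate attributed to SBRT in 17.5.1) and 45 Gy in 6 fractions with no grade 3 or higher toxicity. This stands as to size: 47% cannot be carried over. The documents do not, however, say how long those patients were followed for toxicity, so these figures do not settle the late period.

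A reader might also infer four stronger points that the documents do not support:

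- *Grade 5 is omitted altogether.* It is omitted only for GI toxicity outside the four named conditions.
- *The 47% arose after 6 months.* Section 2.2 reports toxicity among patients alive beyond 6 months; it gives no onset dates.
- *Section 17.3.3 commits the trial to a late-toxicity answer.* It anticipates a "decrease in late gastrointestinal toxicity at one year" relative to single-fraction SBRT, which no arm receives. What it says this population will provide concerns time to progression and treatment planning.
- *The design medians of 6 and 10.2 months show how many in each arm will still attend adverse event visits.* They give modelled progression-free fractions from randomization if the assumed effect is real. Visits are timed from completion of study treatment, and with no effect the arms would not differ.

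**Conclusion.** The point holds for the endpoint as written and should be corrected. It does not show that the trial lacks late safety data. The missing anchor and the cut-off at grade 4 follow directly from the text and need no assumption. That an acute-only endpoint may miss much of the SBRT-related GI toxicity is an inference from one small cohort (7/15, 95% CI 21–73%; 2/15, 2–40%) on a different regimen. The amount missed here cannot be computed from the documents. Because adverse event follow-up stops at removal, including at progression, any late estimate from the planned visits describes events on study, and the report should say so.

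**What to change.** 1. In 17.1.2, 1.2 and the synopsis, extend the second part from grades 3–4 to grades 3–5.
2. Start the window at randomization in both arms.
3. Add the cumulative incidence by arm, to 12 months from randomization, of the same GI events: grade 2 or greater for the four named conditions and grades 3–5 for any other GI toxicity. Use the adverse event assessments already scheduled. Treat death and removal from adverse event follow-up (including at progression) as competing events, and keep the 3-month figure as a component.
4. State that the late estimate covers events before removal.

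**Cost.** This is endpoint and analysis wording, with no change to sample size, visits or the primary analysis. The reported toxicity rate will be somewhat higher. The late estimate is limited to time on study, so a difference between arms may partly reflect how long patients stay on study. With randomization as the start, the 3-month component may also contain little post-SBRT time for late starters. Section 5.3 allows up to 8 weeks between induction and SBRT; if randomization came right at the end of induction, about 13 − 8 = 5 weeks would remain. This is another reason to report the 12-month figure beside it.

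Continuing to collect GI events after progression is optional. Sections 7.4 and 7.5 specify no content for the survival contacts, and section 6.2.1 warns that obstruction, hemorrhage and vomiting are also common with progression, so attribution would be harder.

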17.2 Analysis Populations

Efficacy analysis will be conducted on the intent-to-treat population which includes all randomized patients and on the per-protocol population. The per-protocol population will include patients who have completed 6 or more cycles of mFolfinirox treatment +/- SBRT.

